### **Scope of the study**

**Surgical procedures:** a total of 62 procedures (p=62) belonging to 7 different surgery specialties are involved in this study. Selected specialties are neurosurgery (p=12), orthopedic (p=15), digestive (p=6), urology (p=10), cardiology (p=6), vascular (p=11), multi-specialty (p=2). A brief summary of each procedure will be sent to the participating institution.

**Study type and cohort:** This is a multi-centric prospective study which consists on progressively collecting anonymous data for 15 to 30 procedures from a list of 62 procedures. This study is thus equivalent to a retrospective study. It doesn't require any access to patient medical records nor influence his medical care as the data are only provided by the x-ray system or the medical team.

In order to reach a good compromise between satisfactory statistical power and achievable database, 15 to 30 procedures per surgery type and per institution would be suitable for the study. This is consistent with the previous published studies and recommendations (ICRP, French legislation). Moreover, limiting the number of procedures to this range (15-30) will ensure enrollment of homogeneous cohorts between participating institutions.

73 health institutions of different categories (University hospital, clinic, cancer center, etc..) confirmed their participations to the study. Hence, the minimal number of procedure regardless of the procedure type would be 11490 and the maximal number would be 22980.

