***Revision date: 20/08/2018***

## **Protocol summary**

This study is conducted by a working group of the French Society of Medical Physics (SFPM). Its main aim is to establish reference dose levels for the most common procedures performed in operating rooms using mobile x-ray systems, hence helping medical physicists and surgeons to evaluate their practice and optimize patient radiation protection.

This is a multi-centric prospective study involving 73 medical institutions of different categories (public university hospitals, clinics, cancer centers, etc.). It consists on progressively collecting anonymous data for 15 to 30 procedures from a list of 62 types of procedures, belonging to 7 surgery specialties (neurosurgery, orthopedic, digestive, urology, cardiology, vascular and multi-specialty). Collected data include patient BMI and information about the x-ray equipment, the procedure and the dosimetric parameters. Data collection doesn't require the access to the patient medical record and doesn't impact his medical care.

Proposed dose reference levels will be expressed in terms of KAP (Kerma-Area-Product), fluoroscopy time and air Kerma. Moreover, multiple statistical analyses will be done to investigate the impact of different variables on the procedure X-ray doses.

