### **Data collection**

Data will be collected using a password-protected Excel spreadsheet. This excel file will be sent to all the participating institutions at the beginning of data collection. Every institution will send the excel file completed with anonymized data to the scientific responsible of the study through the secure email server of the APHP institution. Data collection period is set to 6 months.

Collected data have been organized into 4 categories:

- Data regarding the x-ray equipment and available on the quality controls (QC) reports : Year of construction, image detector type, size of the smaller field,

difference between the displayed and measured KAP for the smallest field, size of the biggest field, difference between the displayed and measured KAP for the biggest field, size of the largest field adapted to the size of the phantom, difference between displayed and measured air kerma available in the last QC report, date of the last external QC previous to the procedure. Also, participating institution should precise whether if the x-ray equipment was connected to a Dose Archiving and a Communication system (DACS)

- Data regarding the patient (Optional) : Weight and height (provided from the equipment or given by the medical team)
- Data regarding the procedure: specialty, additional information about the procedure, size of the most used field for the concerned procedure. These data are provided by the medical team.
- Technical and dosimetric data available on the x-ray equipment : total KAP, Total air kerma, total number of image frames, fluoroscopy mode, fluoroscopy pulse rate, fluoroscopy time, dosimetric data specific to the O-arm equipment.

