#### **Outcomes:**

The main goal of this study is to publish descriptive statistics (mean, standard deviation, median, 1st quartile, 3rd quartile) for each dosimetric data (KAP, fluoroscopy time, kerma, etc..) and for each category of surgery procedures. Results will be presented with a 95% confidence interval.

Moreover, correlation analysis between several variables as indicated previously in the goal section will be done. The differences between detector and equipment technologies will be also studied using appropriate statistical tests.

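### Do the planned totals of 11,490 to 22,980 procedures need correcting because the stated inputs do not produce them?

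*Protocol*

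**What the plan says.** All of the sizing text is in the Protocol, under Scope of the study. The scope is "a total of 62 procedures (p=62) belonging to 7 different surgery specialties". The collection target is "15 to 30 procedures per surgery type and per institution would be suitable for the study", introduced with "In order to reach a good compromise between satisfactory statistical power and achievable database" and supported by consistency with earlier published work, ICRP recommendations and French legislation. The participants are "73 health institutions of different categories". The totals follow directly: "Hence, the minimal number of procedure regardless of the procedure type would be 11490 and the maximal number would be 22980".

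The Protocol summary puts the target more briefly, as "progressively collecting anonymous data for 15 to 30 procedures from a list of 62 types of procedures", without saying per type or per institution. Under Data collection, "Data collection period is set to 6 months". Under Outcomes, the main product is descriptive statistics by category of procedure, including the quartiles, and "Results will be presented with a 95% confidence interval".

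**The concern.** The sentence with the totals is worded as a deduction, but the figures just before it do not yield those totals. A reader who multiplies them gets a number about six times too large. A reader who takes the summary literally, as 15 to 30 cases per institution in all, gets one about ten times too small. The only sample-size statement in the document therefore cannot be checked from what it prints.

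Three further doubts follow:

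- The lower total is called minimal, although no rule obliges each site to reach 15 cases of each type within six months.
- Power is claimed without a hypothesis, an effect or an error rate, in a study whose aim is to estimate quartiles.
- A headline above 11,000 could suggest high precision, while each reference level might rest on only about a dozen institutions. If cases within an institution resemble one another, the number of institutions would then limit precision more than the number of cases.

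**Working it through.** **Inputs** (Protocol, Scope of the study): 73 institutions; 62 types (12 + 15 + 6 + 10 + 6 + 11 + 2 = 62, so the breakdown by specialty adds up); m = 15 to 30 cases per type and institution; stated totals 11,490 and 22,980.

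**Step 1. Try to reproduce the totals from the stated inputs.**

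| Product | m = 15 | m = 30 |
|---|---|---|
| 73 x m | 1,095 | 2,190 |
| 62 x m | 930 | 1,860 |
| 73 x 7 specialties x m | 7,665 | 15,330 |
| 73 x 62 x m | 67,890 | 135,780 |
| Stated | 11,490 | 22,980 |

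None matches. 67,890/11,490 = 5.9.

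**Step 2. Solve backwards.** 11,490/15 = 766 and 22,980/30 = 766, both exactly. An arithmetic slip would be unlikely to leave the same whole number at both ends. A common multiplier was evidently used and not printed. Read as combinations of institution and type, it gives 766/73 = 10.5 types per institution and 766/62 = 12.4 institutions per type, or on average 11,490/62 = 185 to 22,980/62 = 371 cases per type. An average of about 10 of the 62 types is believable for institutions of different categories. A full 62 at each is not.

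**Step 3. The word minimal.** The lower total is 766 x 15, the bottom of the planned range. If 10%, 20% or 30% of those cases were not delivered, the total would be 10,341, 9,192 or 8,043. The figure is a planning total, as such figures usually are.

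**Step 4. Does precision depend on institutions and not on cases?** The document gives no intra-institution correlation (ICC), so the values below are assumptions. Effective number per type = (766 x m/62)/(1 + (m - 1) x ICC). This design effect is the one for a mean, so for a third quartile it is only a guide.

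| Assumed ICC | m = 15 | m = 30 | Gain from doubling |
|---|---|---|---|
| 0 | 185 | 371 | 100% |
| 0.05 | 109 | 151 | 39% |
| 0.1 | 77 | 95 | 23% |
| 0.2 | 49 | 55 | 12% |
| 0.3 | 36 | 38 | 7% |

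From about 0.2 upward, the number of institutions dominates. At 0.05 or below, the choice between 15 and 30 matters a good deal. The document does not say which row applies.

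**Step 5. A minimum number of institutions?** The widest distribution-free interval for a third quartile, from smallest to largest value, has coverage 1 - 0.75^n - 0.25^n. This is 0.944 for n = 10 and 0.958 for n = 11, so 11 values are needed for 95%. With 12 values, the interval from the 6th to the 12th has coverage 95.4%. The threshold applies only if the quartile is taken over one value per institution, which the Outcomes section does not say. If the 766 combinations fell at random, so that the institutions per type followed a binomial with 73 trials and probability 766/(73 x 62), the chance of fewer than 11 would be 0.289. Institutions specialise, so random spread is not a realistic model.

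**The case for a change.** The best case for a change runs as follows. The document presents its totals as a deduction, and the deduction cannot be followed. The summary and the cohort sentence omit the unit of collection that the next paragraph supplies. Minimal promises more than the plan secures. Power is the wrong idea for a descriptive study. Repair would take a sentence and a small table, with no extra patients, and would let readers judge how many institutions stand behind each reference level. The protocol makes these statements itself, so a separate analysis plan would not mend them.

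Part of this stands. The multiplier is missing, the summary is looser than the detailed text, and the power phrase has no figure behind it.

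The rest weighs less. The detailed section states the unit plainly, as per type and per institution, and an abbreviated summary does not override it. The roughly 60-fold conflict arises only from setting the two least plausible readings, 1,095 and 67,890, against each other. The document rests its sizing on the count per type and institution, with a stated rationale of feasibility and published practice, and the totals are a by-product. Expected interval widths and the handling of clustering commonly belong in an analysis plan, and none is shown here. Marking types with few institutions as descriptive only would add little where the main output is already descriptive.

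**Conclusion.** No change to the plan follows. The totals cannot be rebuilt from the printed inputs, but they agree exactly with each other through one unstated count, 766. The fault is an omitted input, and no figure is shown to be wrong. Reading 766 as combinations of institution and type is an inference. The averages of 10.5 types per institution and 12.4 institutions per type depend on it, and the number for any one type may be far from the average.

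Supplying the count, calling the totals planned, rewording the power phrase and tightening the summary would each make the text clearer. None would alter which cases are collected, how the quartiles and their 95% intervals are computed, or what is concluded. Analysts will report the numbers of cases and institutions actually obtained for each type, and those numbers, not the planning total, determine precision.

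The claims about precision are conditional. Doubling from 15 to 30 cases raises the effective number by between 7% and 100% across assumed ICCs from 0.3 to 0. The threshold of 11 institutions and the 29% of types below it need institution-level quartiles and random allocation, neither of which the document states.

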### **Inclusion criteria:**

- Fluoroscopy guided procedures performed on adult patients ( $\geq 16$  years old)
- Fluoroscopy guided procedures performed on mobile x-ray systems. Procedures performed outside of the operating rooms using mobile x-ray systems are included in this study
- Fluoroscopy guided procedures performed using mini C-arms or O-arms
- 

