## **Context:**

Reference dose levels, introduced by the International Commission on Radiological Protection (ICRP) in 1996, are intended to help professionals using medical imaging to evaluate their practice and optimize patient's doses.

European directive 2013/59/Euratom emphasizes the need to establish, use and regularly review reference levels for diagnostic and interventional procedures and to publish guidelines on this topic.

Furthermore, national reference levels were established for conventional radiology and CT exams. They are used as a tool for the optimization of medical practices. Besides, a working group of the French society of medical physicists (SFPM) has published in 2017 reference levels for interventional radiology procedures.

Although radiation protection is a big challenge encountered in operating rooms, few data are available in the literature regarding the use of mobile x-ray equipments.

In this context, the SFPM suggested the creation of a working group in 2017 to establish reference levels for the main procedures realized in the operating rooms using mobile x-ray systems. The aim of this working group is to help medical physicists and surgeons in evaluating their practice and optimizing patient radiation protection. The working group is composed of 5 medical physicists working in 5 different institutions in France.

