## **Objectives**

### **Main goal:**

Establish dosimetric reference levels, in terms of KAP (Kerma-Area-Product)

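### The aim names operating-room procedures, eligibility also admits procedures done elsewhere, and no listed data item records where a procedure took place

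*Protocol*

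**What the plan says.** The Protocol summary gives the main aim as reference levels for the "most common procedures performed in operating rooms using mobile x-ray systems". The Context section repeats that scope when it explains why the working group was created: "to establish reference levels for the main procedures realized in the operating rooms using mobile x-ray systems".

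The Inclusion criteria state: "Procedures performed outside of the operating rooms using mobile x-ray systems are included in this study". The Exclusion criteria remove fixed imaging systems even when they stand in the operating theatre. Eligibility therefore turns on whether the equipment is mobile, not on the room. The line under Main goal asks for KAP reference levels and names no setting.

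Under Data collection, the items describing the procedure itself are "specialty, additional information about the procedure, size of the most used field for the concerned procedure". The other three groups cover the x-ray equipment and its quality control, patient weight and height, and technical and dosimetric readings. None of them names the place of the procedure. The Outcomes section reports results by category of surgical procedure, without a split by setting.

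**The concern.** The population that will be analysed is wider than the one named in the aim. The levels are meant to let surgeons and medical physicists judge their own practice. If doses for a given procedure differ by setting, a pooled level could be too high or too low for an operating-room user. The items as listed would not show whether this had happened. The mix of settings could also vary between institutions, which would blur the planned comparisons between sites and institution types.

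This is not a detail that can wait for a statistical analysis plan, because an analysis cannot stratify on a variable that was not collected. The section on study approval says that patients receive no codes and that medical records cannot be accessed. A location missed at data entry could therefore not be recovered from the patient's record.

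**Working it through.** The plan gives no figure on this point to reproduce. The main check sets the sections side by side.

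1. Aim (Protocol summary, Context): mobile x-ray systems and operating rooms.
2. Eligibility (Inclusion and Exclusion criteria): mobile x-ray systems in any room. The aim carries a condition on place that eligibility lacks.
3. Data items (Data collection): four groups, with no item named for place. The only candidate is the open entry for further procedure details, whose content is not specified.
4. Reporting (Outcomes): by procedure category, with settings pooled.
5. Later recovery (Study approval and patients consent): no patient code and no record access.

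To see what pooling could do, take the third quartile, one of the statistics that Outcomes promises. All inputs here are assumptions:

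- KAP within a procedure type is lognormal, with the same log SD *s* (0.7 to 1.1) in both settings.
- A share *f* of cases is done outside operating rooms (10% or 20%).
- The outside median is *r* times the operating-room median (0.5, 0.8, 1, 1.25 or 2).

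With the operating-room median scaled to 1, the operating-room third quartile is exp(0.6745 *s*). The pooled third quartile is exp(*q*), where *q* solves

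(1 − *f*) Φ(*q*/*s*) + *f* Φ((*q* − ln *r*)/*s*) = 0.75.

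Worked case with *s* = 0.8, *f* = 0.10, *r* = 2:

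- Operating-room third quartile: exp(0.5396) = 1.715.
- Solution: *q* = 0.6223. Check: 0.9 × 0.7817 + 0.1 × 0.4647 = 0.750.
- Pooled third quartile: exp(0.6223) = 1.863.
- Ratio: 1.863 / 1.715 = 1.086, a shift of +8.6%.

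Shift in the third quartile over log SD 0.7 to 1.1:

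| Outside/inside median ratio | 10% outside | 20% outside |
|---|---|---|
| 0.5 | -4.6% to -5.3% | -9.3% to -10.7% |
| 0.8 | about -2% | about -4% |
| 1 | 0 | 0 |
| 1.25 | about +2.4% to +2.5% | about +5% |
| 2 | +8.4% to +8.7% | +17.3% to +18.4% |

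At a 5% share, even a twofold ratio gives only about +4%.

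**The case against.** The strongest reply is that the inclusion is a choice, not a slip. It has its own sentence in the Inclusion criteria, the Exclusion criteria draw the boundary by equipment, and the formal main goal names no room. On that reading, the fault is loose wording in two background sections. This largely stands: admitting these cases is not an error. It still leaves the stated aim out of step with eligibility.

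A reader might infer that the settings can never be told apart. The documents do not support that. The medical team supplies the open procedure entry and knows where the case was done, and the spreadsheet template is not shown. What can be said is that an open entry does not secure uniform capture across 73 institutions.

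A reader might also infer that the levels will be biased. That is not shown either. Results are reported by procedure category, so procedure types are not mixed. Detector type, fluoroscopy mode, pulse rate and field size are collected, and part of any setting effect may travel with them. The documents give no reason why the same procedure on mobile equipment should deliver a different dose in another room. A halved or doubled median is a strong assumption, so the larger shifts come from the edge of the grid.

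Finally, one might want operating-room-only levels as the main result. That would reverse the sponsor's stated inclusion choice and is a preference, not a correction.

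**Conclusion.** The point holds as a mismatch of scope with no secured means of checking its effect. The aim names operating rooms, eligibility deliberately does not require them, and no listed item records the setting. Followed as written, the plan yields levels for mobile x-ray systems wherever they are used.

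The size of any effect cannot be known from the documents. Under the assumed shares and ratios, it runs from nil, through about 2% to 5% at modest dose ratios, to about 18% upward or 11% downward at a 20% share with a twofold difference. These figures rest wholly on the assumed shares, ratios and lognormal spread, and they are not evidence of bias. This is a cheap improvement and does not invalidate the study.

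**What to change.** 1. Add one column to the data collection spreadsheet, operating room or outside, completed by the medical team, who already supply the procedure data. It needs no access to medical records.
2. Restate the aim in the Protocol summary and Context as procedures with mobile x-ray systems in any location, so that it matches the Inclusion criteria.
3. Keep the all-location levels as the main result. For procedure types with a material share outside, also report the levels restricted to operating-room cases as a sensitivity analysis.

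The cost is one extra field for each procedure and one extra table. The restricted levels will rest on fewer cases and be less precise.

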### **Secondary goals:**

- Reference levels in terms of fluoroscopy time and air kerma
- Analysis by the procedures details (impact of different techniques, instruments and materials, etc...)
- Assessing inter-site variability
- Correlation between KAP and BMI, fluoroscopy pulse rate and mode

- Ratio between fluoroscopy and radiography doses
- Effect of zoom and magnification on the dose
- Institution -type distribution of doses
- Impact of the surgical specialty on the doses delivered for some procedures.

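### Does the lack of a listed system-type item leave mini C-arm doses inseparable in the KAP reference levels and the equipment comparison?

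*Protocol*

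**What the plan says.** - **Eligibility (Protocol, Inclusion criteria).** One bullet admits procedures on mobile x-ray systems in general. A separate bullet admits "Fluoroscopy guided procedures performed using mini C-arms or O-arms".
- **Equipment data (Protocol, Data collection).** The equipment items begin with "Year of construction, image detector type, size of the smaller field". They go on to further field sizes, differences between displayed and measured KAP and air kerma, the date of the last external quality control, and whether the unit is linked to a dose archiving system. No item names the class of system, the make or the model.
- **Other data (same section).** The procedure items include "additional information about the procedure" and the most used field size. The technical items end with "dosimetric data specific to the O-arm equipment".
- **Timing (same section).** "This excel file will be sent to all the participating institutions at the beginning of data collection".
- **Analysis (Protocol, Outcomes).** Descriptive statistics are reported "for each category of surgery procedures", and differences between detector and equipment technologies are to be tested. No split by class of system is stated.

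**The concern.** The protocol gives mini C-arms and O-arms their own inclusion bullet, so it treats them as distinct from ordinary mobile systems. It then plans a comparison of equipment technologies. A reader who goes through the itemised data, which is detailed enough to include the date of the last external quality control, finds nothing that says which class of system was used. O-arms can be recognised from their own item; mini C-arms have no counterpart.

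Two things would be at stake:

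- The technology comparison would have to identify mini C-arms by proxy.
- For a procedure done on more than one class of system, the third quartile of KAP could depend on which systems the contributing sites own, and the listed data could not show by how much for mini C-arms.

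An analysis plan can add a split, but it cannot create a variable that was never recorded. One column is also cheaper before the file goes out than a query to every unit afterwards.

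**Working it through.** **1. Is the list the full form?** Compare the listed items with what the stated analyses require.

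| Needed for | Variable | Named under Data collection? |
|---|---|---|
| Every reference level | Procedure type | No (specialty only) |
| Inter-site variability | Institution | No |
| Distribution by institution type | Institution category | No |
| Detector comparison | Detector type | Yes |
| Separating O-arms | O-arm dosimetric item | Yes |
| Separating mini C-arms | Class of system | No |

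The first three must be on the form, or the study could report nothing. The list is therefore a summary, and absence from it is weak evidence that a column is missing.

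**2. Do the stated analyses require the class of system?** The Outcomes section does not define equipment technology as standard C-arm against mini C-arm against O-arm. Detector type, year of construction, fluoroscopy mode and pulse rate are all listed and support a comparison as worded. The secondary goal "Analysis by the procedures details (impact of different techniques, instruments and materials, etc" concerns details of the procedure, not the x-ray unit, so it does not add to the need.

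**3. What identifies a mini C-arm if no column exists?** Four field-size items (smallest, biggest, phantom-adapted, most used), detector type, and the additional procedure information. Nothing in the protocol shows that these would fail.

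**4. How large could the effect on the main result be?** The protocol gives no dose ratio, spread or share by class, so everything after the first bullet rests on assumptions.

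- *Sites per procedure.* The Scope section says "the minimal number of procedure regardless of the procedure type would be 11490 and the maximal number would be 22980". 11490/15 = 766 and 22980/30 = 766 site-by-procedure sets, so the two totals agree with each other. 766/62 = 12.35 sites per procedure on average.
- *Share s of another class* (equal cases per site, one class per site). One site: 1/12.35 = 8.1%. Two sites: 2/12.35 = 16.2%.
- *Bounds for any distributions.* The pooled distribution is F = (1 - s)F0 + sG, where F0 is the main system, G the other class, and G lies between 0 and 1. At the pooled third quartile, F0 therefore lies between (0.75 - s)/(1 - s) and 0.75/(1 - s). One site: 0.728 to 0.816. Two sites: 0.702 to 0.895.
- *Specific ratios*, assuming log-normal KAP with log-SD 0.9 in both classes, solving F(q) = 0.75:

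| KAP ratio, other class to main | One site | Two sites |
|---|---|---|
| 0.1 | -5.9% | -12.2% |
| 0.5 | -4.1% | -8.2% |
| 1 | 0 | 0 |
| 3 | +11.4% | +24.7% |

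- *Sampling error without clustering.* SE of the log third quartile = 0.9 × √(0.75 × 0.25/n)/φ(0.674), with φ(0.674) = 0.318. For n = 12.35 × 15 ≈ 185, SE = 0.090 and the 95% interval is -16%/+19%. For n = 12.35 × 30 ≈ 371, SE = 0.064 and the interval is -12%/+13%.
- *Sampling error with clustering*, by simulation of the third quartile with 12 sites and log-SD 0.9:

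| Assumed intraclass correlation | 15 cases per site | 30 cases per site |
|---|---|---|
| 0.1 | -21%/+26% | -19%/+22% |
| 0.2 | -25%/+32% | -23%/+29% |

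Every one-site shift lies inside even the unclustered intervals. The two-site shift at a ratio of 3 (+24.7%) lies outside the unclustered intervals. It lies inside both clustered ranges at a correlation of 0.2. At 0.1 it is inside with 15 cases per site and just outside with 30.

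**The case for a change.** The strongest case for a change is that this is a data-capture question, not one an analysis plan can settle. The protocol separates these systems when it defines eligibility, commits to an equipment comparison, lists a dedicated item for O-arms and lists none for mini C-arms. A shift from the mix of systems is also systematic: more cases narrow the sampling interval but leave the shift in place. Adding a column before distribution costs almost nothing.

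Part of this stands. No class-of-system item is named, an unspecified information field is no substitute for a required one, and sampling error does not excuse a systematic effect. Comparing the shift with the interval shows only that it would seldom alter how a published level is read.

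The rest does not carry. The step from not being listed to not being collected fails, because indispensable variables are unlisted too. The mix of systems is also part of what an all-systems reference level describes, so the pooled figure is not biased for its stated target. The ratio of 3 is not tied to mini C-arms by anything in the protocol; if it belonged to O-arms, those cases can already be set apart. Rules for reporting by class, minimum numbers of sites, and results with and without certain systems are normal content of an analysis plan, which is not shown here.

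**Conclusion.** The observation is correct as a reading of the text, but no change to the plan follows. It is a gap in a summary list, limited to one sub-class of equipment and to a secondary comparison whose wording does not require that sub-class to be separated. Detector type and four field-size items give analysts a reasonable route to it. The main KAP levels over all eligible systems are valid for the stated scope, and procedures done on a single class of system are unaffected.

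The illustrative shifts in the third quartile are -6% to +11% for one site in about 12 and up to about +25% for two sites at three times the KAP. These rest on assumed log-normal doses with log-SD 0.9, equal cases per site and an even spread of sites over the 62 procedures. Only the two-site case approaches or exceeds sampling error, and whether it does so depends on the assumed clustering.

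The investigators may wish to confirm that the spreadsheet records the class of system and to name it in the Data collection section. That is a clarification at their discretion; the protocol can be carried out without it.
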